2.1 Primary Objectives

Child Participants (Aim 1):

1. To examine the effects of the Building Resilience Program (BRP) on coping skills, engagement, self-regulation, emotional health, quality of life, and stress in preschool participants aged 24-66 months with history of ACEs
2. To evaluate the effectiveness of Goal Attainment Scaling (GAS) as a measurement tool for tracking individual progress and changes pre-post intervention

Caregiver Participants (Aim 2):

3. To examine the effects of the Building Resilience Program on caregiver resilience, emotional management, and coping strategies
4. To assess caregiver satisfaction with program methods and outcomes

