2.2 Primary Hypotheses

Child Participants:

- All child participants will demonstrate improved coping skills, engagement, quality of life, self-regulation, and emotional health by the end of the intervention period as measured by standardized assessments and individualized Goal Attainment Scaling
- GAS will prove an effective tool for capturing individualized therapeutic change in trauma-exposed preschoolers

Caregiver Participants:

- Caregivers participating in the BRP will demonstrate improved resilience and coping strategies as measured by standardized self-report assessments
- Caregivers will report high satisfaction with program methods and perceived benefits for both themselves and their children

3. Background and Rationale

Children living in under-resourced, poverty-stricken neighborhoods face significantly elevated risks for adverse childhood experiences (ACEs) and trauma. The study location serves neighborhoods where 36.5-41.6% of residents live in poverty (compared to 11.9% nationally), with 52.8-54.9% of children living in poverty. The Early Learning Center annual data indicates 97% of children come from single-parent households, 88% live in poverty, 51% report 1-5 ACEs, and 14% report 6-10 ACEs.

Preschool-aged children (ages 3-5) are particularly vulnerable to ACEs impacts due to rapid brain development and critical socioemotional growth occurring during this period. Recent neurobiological research demonstrates that toxic stress during preschool years can significantly alter developing brain architecture, particularly in regions associated with executive function, emotion regulation, and stress response systems.

The American Academy of Pediatrics identifies the critical need for interventions that build resilience and address maladaptive responses due to toxic stress from ACEs. Occupational therapists are well-suited to integrate trauma-informed care into service delivery through their expertise in occupation-based interventions, particularly using play as the primary occupation for young children.

4. Study Design

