7.1.2 Goal Attainment Scaling (GAS)

Domains: Three individualized goals per participant

- Behavior
- Engagement/Participation
- Resilience

Scoring: -2 (much worse than expected) to +2 (much better than expected outcome) **Frequency:**

Weekly observations during both intervention and control periods **Conversion:** Raw scores converted to T-scores (M=50, SD=10) for statistical analysis

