8.2.2 Primary Analysis - Goal Attainment Scaling

Data Conversion: Individual GAS scores converted to T-scores (M=50, SD=10)

Baseline Comparisons: Independent samples t-tests for GAS T-scores across three domains

Primary Efficacy Analysis: ANCOVA comparing IG1 (weeks 0-7) vs. IG2 (weeks 7-14)

- Covariates: Baseline domain differences, IG2 control period changes
- Combined score calculated by averaging three domain T-scores

Secondary Analysis:

- Within-group paired samples t-tests for intervention effects
- Maintenance analysis for IG1 (weeks 8-14)
- Clinical significance threshold: 10+ T-score point improvements

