9.3 Data Quality Assurance

- Regular data monitoring for completeness and accuracy
- Inter-rater reliability checks for GAS observations
- Standardized training for all data collection staff

10. Ethical Considerations

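### Primary objective 2, whether GAS works as a measurement tool, has no planned analysis or success criterion that can answer it

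*Combined protocol and SAP*

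**What the plan says.** Section 2.1 gives as the second primary objective "To evaluate the effectiveness of Goal Attainment Scaling (GAS) as a measurement tool", for following each child's progress from before to after the intervention. The matching hypothesis in section 2.2 is that "GAS will prove an effective tool for capturing individualized therapeutic change in trauma-exposed preschoolers". Neither section says what result would count as success.

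Section 7.1.2 sets one goal in each of three domains, scored on a five-level scale, with "Weekly observations during both intervention and control periods" and "Raw scores converted to T-scores (M=50, SD=10) for statistical analysis".

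Section 8.2.2 then lists the GAS analyses:
- baseline t-tests;
- a primary "ANCOVA comparing IG1 (weeks 0-7) vs. IG2 (weeks 7-14", with baseline domain differences and IG2 control-period change as covariates;
- within-group paired t-tests;
- a maintenance analysis for IG1;
- a threshold of 10 or more T-score points for clinical significance.

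Outside the analysis plan, section 9.1 has research team members record GAS and therapy leads review the scoring each week. Section 9.3 lists "Inter-rater reliability checks for GAS observations", and section 11.2 adds rater training. No blinding of GAS raters is stated.

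**The concern.** Section 2.2 also names GAS as one of the measures by which children are expected to improve. A rise in GAS could therefore be cited both for the program and for the instrument. To support the instrument, the plan needs something beyond the rise itself: evidence that GAS behaves differently under BRP and under control, that it relates to other measures of the same children, or that raters agree. None of these is planned as an analysis.

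At stake is one of the stated primary objectives. Section 15.1 also commits GAS methodology findings to the primary publication. Without a criterion or a suitable contrast, a conclusion about GAS would rest on score changes that true improvement, rating error or lenient goals could all produce.

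**Working it through.** The plan gives no figure for objective 2 (no reliability coefficient, responsiveness index or success rule), so there is none to reproduce.

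**Step 1. What each planned GAS analysis can show**

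| Analysis in 8.2.2 | What is compared | Bearing on objective 2 |
|---|---|---|
| Baseline t-tests | IG1 vs IG2 before treatment | Balance only |
| Main ANCOVA | IG1 weeks 0-7 vs IG2 weeks 7-14 | BRP vs BRP: section 4.2 gives BRP to IG1 in Phase 1 and to IG2 in Phase 2 |
| Paired t-tests | Before vs after BRP, within group | Change, cause not identified |
| IG1 maintenance | Weeks 8-14 | Persistence of score |
| 10-point threshold | Size of individual gain | Change, cause not identified |

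No row compares BRP with concurrent control, although GAS is rated weekly in both conditions (7.1.2, 7.2). IG2 control-period change enters only as a covariate.

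**Step 2. Why change alone is weak evidence (illustration)**

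Assume T = 50 + 10x for a single goal with score x, in line with the stated mean and SD. One scale step is then 10 T-points, which equals the clinical-significance threshold. In the three-domain average, one step on one goal is 10/3 = 3.3 points.

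*Random rating error, no true change.* Take the SD of a pre-post difference as 10 × √(2(1 − ICC)) and a normal approximation to the five-level scale.
- ICC 0.8: SD = 10 × √0.4 = 6.32; P(gain ≥ 10) = 1 − Φ(10/6.32) = 0.057, about 6% of children.
- ICC 0.6: SD = 10 × √0.8 = 8.94; P = 1 − Φ(10/8.94) = 0.132, about 13%.

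*Shared upward drift of half a level (5 points), no true change.* Use a one-tailed paired t-test at 0.05, with noncentrality (5/SD) × √n.

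| n | Rejects at SD 10 | Range for SD 14.1 to 6.3 |
|---|---|---|
| 8 | 36% | 23-65% |
| 10 | 43% | 27-75% |
| 16 | 60% | 39-92% |

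The sizes 8 and 10 are the per-group figures in section 8.3; 16 is half of the 32 in section 5.2. ICC, drift and SD are assumptions. One-tailed testing is stated in 8.2.1 for the standardised measures and assumed here for GAS.

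**Step 3. What the available data could deliver**

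Section 8.3 gives 17-19 complete cases (8-10 per group) for the primary ANCOVAs.

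*Phase 1 standardised difference.* Near zero, before any gain from baseline adjustment, SE ≈ √(2/n) for n per group. At n = 8, 1.96 × √(2/8) = 0.98. At n = 10, 1.96 × √(2/10) = 0.88. The 95% CI is thus about ±0.9 to ±1.0 SD.

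*Correlation of changes.* The Fisher interval is tanh(atanh r ± 1.96/√(n − 3)), with atanh 0.5 = 0.549.
- n = 17: 0.549 ± 0.524, giving 0.03 to 0.79.
- n = 19: 0.549 ± 0.490, giving 0.06 to 0.78.
- n = 32: 0.549 ± 0.364, giving 0.18 to 0.72. This is optimistic given section 8.3.

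*ICC.* For two raters under a one-way model, the F-based 95% CI for an ICC of 0.80 is 0.55-0.92 with 18 children and 0.63-0.90 with 32.

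**The case against.** The best defence is that objective 2 is narrow: it concerns tracking individual progress before and after the intervention. Paired tests, the maintenance analysis and the 10-point threshold bear on that wording, and flat GAS scores would count against the hypothesis. This stands. A reader might infer that the hypothesis rests on a test that cannot refute it; that goes too far. The tests are non-specific rather than irrefutable.

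A reader might also infer that the plan will declare objective 2 met whenever the GAS efficacy result is positive. No section says so. What can be shown is the absence of a criterion, not a circular decision rule.

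The plan does not ignore raters: training, weekly review and inter-rater checks are all listed. These are quality-assurance steps with no statistic, sample or threshold. It would be tempting to assume they yield duplicate ratings ready for an ICC, but section 9.3 does not say that independent paired scores were made or kept, and the weekly review may be supervisory only.

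Finally, the remedy has limits. An ICC does not detect expectancy shared by all raters. The Phase 1 contrast uses research-team raters whose blinding is not stated. A low correlation with generic caregiver-report scales is ambiguous: GAS may be poor, or it may capture individual change those scales miss. All of this stands, and it limits what the added analyses may claim.

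**Conclusion.** The point holds in limited form. Objective 2 has no analysis or success criterion that can answer it. The main GAS ANCOVA cannot show that GAS separates BRP from control, and the inter-rater checks are not tied to the objective. This follows from sections 2.1, 2.2, 4.2, 8.2.2 and 9.3 without any numerical assumption.

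The figures in Step 2 illustrate only how far change scores can mislead; they depend on assumed ICC, drift, SD and T-score formula. The documents do not show that GAS ratings are in fact biased or that goals were easy, and no such conclusion should be drawn.

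The plan should be changed, but the change improves the evidence on GAS without settling it. With 17-19 complete cases every added estimate will be imprecise.

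**What to change.** Add a paragraph for objective 2 to section 8.2.2:

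1. **Main estimate.** The concurrent Phase 1 (weeks 0-7) IG1 versus IG2 baseline-adjusted standardised difference in GAS with 95% CI, shown beside the same contrast for PROMIS and PedsQL in the same children.
2. **Supporting estimate.** The correlation of week 0-7 GAS change with PROMIS and PedsQL change, with CI, noting that a low value is ambiguous for an individualised measure.
3. **Conditional estimate.** An ICC with CI per domain, only if independent paired ratings exist. If they do not, say so.
4. **Interpretation.** State that neither a within-group rise in GAS nor the BRP-versus-BRP ANCOVA is by itself evidence for objective 2. State also that expectancy shared by raters and lenient goal setting remain unresolved, because no blinding of GAS raters is stated.
5. **Status.** Label the additions post hoc: the document already reports achieved enrolment (5.2), post-hoc power (8.1) and analysed sample sizes (8.3).

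Items 1 and 2 use ratings and questionnaires already scheduled in sections 7.1.2 and 7.2, so the cost is a short analysis and one paragraph. The cost of item 3 depends on whether paired ratings were kept. The downside is wide intervals and a more cautious conclusion on GAS.

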2.2 Primary Hypotheses

Child Participants:

- All child participants will demonstrate improved coping skills, engagement, quality of life, self-regulation, and emotional health by the end of the intervention period as measured by standardized assessments and individualized Goal Attainment Scaling
- GAS will prove an effective tool for capturing individualized therapeutic change in trauma-exposed preschoolers

Caregiver Participants:

- Caregivers participating in the BRP will demonstrate improved resilience and coping strategies as measured by standardized self-report assessments
- Caregivers will report high satisfaction with program methods and perceived benefits for both themselves and their children

3. Background and Rationale

Children living in under-resourced, poverty-stricken neighborhoods face significantly elevated risks for adverse childhood experiences (ACEs) and trauma. The study location serves neighborhoods where 36.5-41.6% of residents live in poverty (compared to 11.9% nationally), with 52.8-54.9% of children living in poverty. The Early Learning Center annual data indicates 97% of children come from single-parent households, 88% live in poverty, 51% report 1-5 ACEs, and 14% report 6-10 ACEs.

Preschool-aged children (ages 3-5) are particularly vulnerable to ACEs impacts due to rapid brain development and critical socioemotional growth occurring during this period. Recent neurobiological research demonstrates that toxic stress during preschool years can significantly alter developing brain architecture, particularly in regions associated with executive function, emotion regulation, and stress response systems.

The American Academy of Pediatrics identifies the critical need for interventions that build resilience and address maladaptive responses due to toxic stress from ACEs. Occupational therapists are well-suited to integrate trauma-informed care into service delivery through their expertise in occupation-based interventions, particularly using play as the primary occupation for young children.

4. Study Design

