4.1 Study Type

Randomized controlled trial with waitlist control design. *Original program was designed for two, 8-week sessions totaling 16 weeks. Unforeseen circumstances (a flood at the facility) shortened the available study period to 14 weeks, so the control condition was shortened and the content condensed and combined to maintain intervention integrity.

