4.2 Study Design Overview

- Phase 1: Intervention Group 1 (IG1) receives BRP intervention for 7 weeks while Intervention Group 2 (IG2) receives standard care (waitlist control)
- Phase 2: IG2 receives BRP intervention for 7 weeks while IG1 continues standard care activities
- Total study duration: 14 weeks

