8.2 Statistical Methods

8.2.1 Primary Analysis - Standardized Measures

Baseline Comparisons: Independent samples t-tests for continuous variables to assess randomization success

Primary Efficacy Analysis: Analysis of Covariance (ANCOVA)

- Independent Variable: Group assignment (IG1 intervention vs. IG2 waitlist control)
- Dependent Variables: Week 7 standardized assessment scores
- Covariates: Baseline scores, any maturation effects identified in IG2 waitlist period
- Effect sizes: Cohen's d with 95% confidence intervals

Secondary Analysis: Paired samples t-tests for within-group changes

- One-tailed tests for intervention effects (directional hypotheses)
- Two-tailed tests for control period effects

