13.2 Implemented Modifications

Duration Change: Original 8-week intervention modified to 7 weeks due to facility closure from flooding

- All content maintained with combined final caregiver-child session
- Timeline adjustments documented and approved

14. Study Timeline

Phase	Duration	Activities
Recruitment	2 months	Participant enrollment, consent, baseline assessments
Phase 1	7 weeks	IG1 intervention, IG2 waitlist control
Assessment	1 week	Mid-study assessments
Phase 2	7 weeks	IG2 intervention, IG1 standard care
Final Assessment	1 week	Final assessments, study conclusion
Analysis/Reporting	3 months	Data analysis, manuscript preparation

15. Publication and Dissemination Plan

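### The primary child hypothesis is a before-after statement with no comparator, so the tests that match it cannot separate BRP from natural development

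*Combined protocol and SAP*

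**What the plan says.** Section 2.1 sets a causal objective for the children: "To examine the effects of the Building Resilience Program (BRP) on coping skills, engagement, self-regulation, emotional health, quality of life, and stress". Section 4.1 describes the study as a "Randomized controlled trial with waitlist control design", and 4.2 has IG1 on BRP for the first 7 weeks while IG2 waits on standard care, after which the groups switch.

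The hypothesis in 2.2 is worded differently: "All child participants will demonstrate improved coping skills, engagement, quality of life, self-regulation, and emotional health by the end of the intervention period". It covers both arms, describes change over time and mentions no control. It is to be judged on the standardized assessments and on GAS.

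Section 8.2 then plans three kinds of test:

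- Standardized measures, primary (8.2.1): ANCOVA of week-7 scores, IG1 on BRP against IG2 on the waitlist. The covariates are baseline and whatever maturation is found in IG2 while it waits.
- GAS, primary (8.2.2): ANCOVA of IG1 in weeks 0-7 against IG2 in weeks 7-14.
- Secondary: paired t-tests within group. In 8.2.1 they are one-tailed for the intervention period; 8.2.2 lists "Within-group paired samples t-tests for intervention effects" without stating sidedness.

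Alpha is 0.05 throughout (8.4). Section 8.3 gives 8-10 children per group for the primary ANCOVAs.

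**The concern.** The objective and the design ask whether children do better with BRP than without it. The hypothesis asks only whether children are better at the end than at the start. These can have opposite answers: if both arms improve equally, the hypothesis is met on its ordinary group reading while the randomised difference is zero.

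The plan leaves room for change without BRP. Section 3 describes this age as one of "rapid brain development and critical socioemotional growth occurring during this period", and 8.2.1 provides for maturation in the waitlist group. The tests that fit the wording of 2.2 are uncontrolled, yet their label attributes the change to the intervention.

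The conflict could well arise. Section 8.1 reports observed power below 20% for the standardized measures, so a non-significant week-7 contrast beside significant paired tests is plausible. No sentence in Section 8 says which result decides the hypothesis in 2.2. What is at stake is whether change that may be natural gets credited to BRP.

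**Working it through.** **Step 1. Match each planned test to the question it answers.**

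| Test | Comparison | Untreated comparator? | Matches 2.2 as worded? |
|---|---|---|---|
| Week-7 ANCOVA (8.2.1) | IG1 after BRP vs IG2 before BRP | Yes, concurrent and randomised | No: IG2 has not yet had BRP |
| GAS ANCOVA (8.2.2) | IG1 BRP period vs IG2 BRP period | No: both sides on BRP, in different weeks | No: it compares two BRP periods |
| Paired t-tests (8.2.1, 8.2.2) | Start vs end of BRP within one arm | No | Yes |

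The GAS row deserves emphasis. A fully effective programme and an inert one could both give a null result there. Adjusting for IG2's control-period change does not help, because IG1 has no waitlist period and the comparison remains BRP against BRP. For IG2's own BRP period no untreated group is left, since IG1 has already been treated (4.2).

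**Step 2. How often a paired test is significant when BRP does nothing.** The plan states no figure to reproduce here. Inputs: one-tailed alpha 0.05 (8.2.1, 8.4) and n = 8-10. That n is given in 8.3 for the ANCOVA groups and is assumed here for the paired tests, whose own n is not stated. The true BRP effect is zero. The natural change m, in SDs of the change score, is an assumption: the documents give no rate and do not say whether scores are age-normed.

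The paired statistic follows a noncentral t distribution with n - 1 degrees of freedom and noncentrality m√n. The test is significant when it exceeds the 95th percentile of the central t. For n = 9 and m = 0.5, the noncentrality is 0.5 × 3 = 1.5, the critical value on 8 degrees of freedom is 1.860, and the probability is 0.393.

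| n | m = 0 | m = 0.2 | m = 0.3 | m = 0.5 | m = 0.8 |
|---|---|---|---|---|---|
| 8 | 5% | 12.9% | 19.0% | 35.7% | 65.3% |
| 9 | 5% | 13.7% | 20.6% | 39.3% | 70.7% |
| 10 | 5% | 14.5% | 22.2% | 42.7% | 75.4% |

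**Step 3. The same drift in the randomised comparison.** A simulation used 8,000 runs per setting, 9 children per group, an assumed baseline to week-7 correlation of 0.6, zero BRP effect and the same drift in both arms. The ANCOVA was two-sided and adjusted for baseline only.

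| m | Week-7 ANCOVA | One-tailed paired test, IG1 |
|---|---|---|
| 0 | 4.9% | 4.6% |
| 0.3 | 4.8% | 20.3% |
| 0.5 | 5.1% | 39.5% |
| 0.8 | 5.0% | 70.5% |

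Drift shared by both arms cancels in the concurrent contrast and does not cancel in the paired test.

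**The case against.** The strongest reply is that the plan already ranks its analyses. Section 8.2.1 names the week-7 ANCOVA as the primary efficacy analysis, and both 8.2.1 and 8.2.2 make the paired tests secondary. This stands for the standardized measures. A reader might infer that following the plan leads to an efficacy claim from paired tests despite a null ANCOVA; in fact that would depart from the stated ranking. It does not help GAS, whose primary analysis has no untreated side, and it leaves 2.2 unaligned with the ranked tests.

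Second, maturation is only allowed for. Section 8.2.1 speaks conditionally, and Section 3 is explaining vulnerability to adverse experiences, not giving a growth rate for any scale over 7 weeks. Age-normed scores would drift less. So natural improvement is possible, not established.

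Third, a reader might take the hypothesis literally, as a claim about every child, and say that growth easily satisfies it. It would not. With a normally distributed change averaging 0.5 SD, each child improves with probability 0.691, so all improve with probability 0.691^8 = 5.2% or 0.691^10 = 2.5%. No planned analysis tests that claim. The point here rests on the group-mean reading.

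Fourth, a reader might add regression to the mean, settling in at school, or a longer development interval in IG1 because Section 14 puts baseline assessments in a 2-month recruitment phase. The documents do not support these. Sections 5.3 and 5.4 set no score threshold, 4.3 refers to classrooms that already existed, and 7.2 places baseline at Week 0.

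Finally, a significant paired test under real growth is not a false positive for the hypothesis as written. It becomes an error only when the change is attributed to BRP, which is what the label invites.

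**Conclusion.** The mismatch is real and worth correcting. The randomised design and the week-7 ANCOVA can address the BRP effect on the standardized measures. The faults are in the wording of 2.2, in the label on the paired tests, and in a primary GAS comparison without an untreated group.

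With zero BRP effect, a one-tailed paired test would be significant in about 19-22% of cases at a drift of 0.3 SD of the change score and 36-43% at 0.5 SD, against a nominal 5%. These rates rest on an assumed drift and on 8-10 children per paired test. They show how such a test behaves; they do not estimate what happened in this trial. Larger paired samples would raise the rates, but the documents do not state the paired n, so no such figures are relied on.

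**What to change.** 1. In 2.2, restate the hypothesis as a comparison of group means: *at week 7, children assigned to IG1 will score better on average than children assigned to IG2, adjusted for baseline*. Delete *All*.
2. In 8.2, state that efficacy is concluded only from the concurrent IG1 against IG2 comparison, for the standardized measures and for GAS. GAS needs no new data: 7.1.2 and 7.2 provide an initial score and weekly observations in both arms, in intervention and control periods alike.
3. In 8.2.1 and 8.2.2, relabel the paired tests as *change during the BRP period (BRP plus natural development)* and make them descriptive only.
4. Date the change and disclose it as a clarification made after data were seen. Section 5.2 already reports the achieved enrolment and analytic sample, and 8.1 reports post-hoc power and effect sizes.

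The cost is a reworded hypothesis, a few lines in 8.2 and a changed primary comparison for GAS. The downside is that positive paired results can no longer be presented as evidence of efficacy, which leaves that conclusion to a small randomised comparison.
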